Approximately 150 subjects whose constipation is confirmed during the Screening Period will be randomized in the Double-Blind Treatment Period to receive either lubiprostone or matching placebo BID. Others whose constipation does not satisfy the criteria during the 14-day Screening Period or those who receive a rescue medication within 24 hours prior to the first dose on Day 1 are ineligible for randomization in the Double-Blind Treatment Period and therefore will be excluded from the study. Subjects who satisfy the inclusion criteria and do not meet the exclusion criteria are randomized to 1 of the treatment groups in the order of the number assigned. Approximately 150 subjects with CIC will be randomized to 2 groups: active treatment or placebo in a 1:1 ratio (75 subjects each) in a double-blinded manner.

[figure not shown]
Subjects will be instructed to take 1 capsule BID, orally, at the same time of day, preferably in the morning with breakfast and in the evening with dinner. Subjects are to begin their study drug treatment in the morning with breakfast following Visit 2.

Subjects will return to the study site on approximately Study Days 8, 15, and 29 during the 4 weeks of double-blind treatment and will be followed for an additional 2 weeks during the Follow-Up Period, in which no treatment will be administered.

At the investigator's discretion, with consideration to subject's bowel movement frequency and consistency, dose adjustments (dose reduction) may be made in a double-blind manner. Dose adjustment should be documented in the subject's source notes. Procedure for reduction of study drug dose due to Adverse Events is described in Section 7.7.

Subjects who withdraw prematurely will be seen within 1 week of discontinuation for an Early Termination Visit. A schematic of the study design is included as Figure 6.a. A schedule of assessments is listed in Appendix A.

Figure 6.a Schematic of Study Design

Note: Randomization occurs on Day -1 of the Screening Period. The first dose of study drug is administered the next day, on Day 1 of the Double-Blind Treatment Period.

Note: There is no treatment during the Follow-up Period.

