# 13.1.3.1 Primary Endpoint

The primary endpoint for the study is the frequency of SBM at Week 1. An SBM is defined as any BM that does not occur within 24 hours after rescue medication use. The SAP will contain more details on the handling of rescue medication and missing or partial data.

In order to adjust for early withdrawals, weekly SBM frequency rates will be calculated as follows:

(Number of SBMs / Number of Days) 
$$\times$$
 7

The number of days in the denominator above is the number of days during the week that the subject was in the study. Weeks will be calculated as 168-hour intervals starting with the exact time of the first intake of study drug. The number of days will generally be 7 unless a subject drops out during a treatment week. If the number of days is less than 4, then the data will be considered insufficient and the rate will be set to missing.

The primary endpoint will be analyzed using van Elteren's test stratified by center to examine the difference between lubiprostone and placebo. Additionally the endpoint will be analyzed using analysis of variance (ANOVA) models with center and treatment in the model as a sensitivity analysis. The estimated least squares (LS) means, related mean difference and associated 95% CI will also be presented to aid interpretation of the clinical effect. The interaction between treatment and center will also be examined in a separate ANOVA model.

This endpoint will be analyzed for the FAS. A sensitivity analysis using the PP will also be presented.

To examine the effects of any dose reduction in response to an AE an additional sensitivity analysis will also be performed. This will be performed on the FAS where data from those subjects with a dose reduction will be excluded from the time of dose reduction and subjects will be treated as a drop-out from this time point onwards. Additionally, another factor will be added to the ANOVA model to examine the effect of dose reduction, this will be performed on the FAS, with no subjects excluded.

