# 6.0 DETERMINATION OF SAMPLE SIZE

Assuming equal allocation, a power of 90%, an alpha level of 0.05 for a 2-sided test, a placebo mean of 4 (standard deviation of 2.7), and a treatment mean of 5.9 (standard deviation of 4) for SBM frequency at Week 1 and using the Wilcoxon-Mann-Whitney test [1], a total sample size of 146 is required. The Wilcoxon-Mann-Whitney test is a non-parametric test of the null hypothesis that the distribution is the same for both placebo and treatment responses against the alternative that there is a location difference between the two. The primary analysis will be conducted using the van Elteren test, which is a stratified version of the Wilcoxon-Mann-Whitney test, use of the Wilcoxon-Mann-Whitney test for sample size estimation will provide an approximate sample size for the van Elteren analysis. The estimates of placebo and treatment response are based on a previous study conducted by Sucampo Pharmaceuticals in the United States of America (Protocol No. RTU/0211SC0131).

The primary endpoint requires subjects to complete at least 4 days of the study diary, therefore assuming a non-evaluable rate of 3% by Day 4 an additional 4 subjects are required, giving a total of 150 subjects.

1 5

	CROSS-REGIONAL TEMP	LATE	
Template Number:	C-TMPL-DO-801	Page:	12 of 31
Version Number:	1.2	Effective Date:	14 Sep 201
This version replaces	s: 1.1		
Parent Document:	C-SOP-DO-800		
Template Title:	Statistical Analysis Plan (Legacy Takeda)	)	

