# Sensitivity Analyses

The primary analysis as described above will be repeated using the PP rather than the FAS. An additional sensitivity analysis using the FAS assuming a 'worse-case' scenario approach will also be conducted, where missing values, including those with < 4 days diary data, are assigned the worst case values (the lowest SBM frequency for week 1) recorded in the study by any subject for that endpoint at that time.

Additionally the endpoint will be analyzed using robust analysis of variance (ANOVA) models (by M-estimation [3] using PROC ROBUSTREG in SAS) with center and treatment in the model as a sensitivity analysis using the FAS. The interaction between treatment and center will also be examined in a separate model, using robust ANOVA methods as previously described.

To examine the effects of any permanent dose reduction in response to an AE (as recorded on the eCRF) an additional sensitivity analysis will also be performed. This will be performed on the

CROSS-REGIONAL TEMPLATE			
Template Number:	C-TMPL-DO-801	Page:	22 of 31
Version Number:	1.2	Effective Date:	14 Sep 2015
This version replaces:	1.1		
Parent Document:	C-SOP-DO-800		
Template Title: St	tatistical Analysis Plan (Legacy Takeda)		

FAS where data from those subjects with a dose reduction will be excluded from the time of dose reduction (taken as date of last BID dose + 12 hours, e.g. if the evening dose is removed then the time will be from the morning dose + 12 hours, if the morning dose is removed then it will be from the previous day's evening dose + 12 hours) and subjects will be treated as a dropout from this time point onwards. This will be implemented using robust ANOVA. Additionally, another factor will be added to the robust ANOVA model to examine the effect of dose reduction (), this will be performed on the FAS. This analysis will not be carried out if the number of subjects with a dose reduction within the first week is less than 5%.

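### Dose reduction, a post-randomisation event, is entered as a factor in the Week 1 SBM model: its coefficient cannot show the effect of reduction, and the treatment coefficient beside it can be biased

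*SAP*

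**What the plan says.** The primary analysis (SAP 7.8.1) is a van Elteren test of Week 1 SBM frequency, stratified by center, on the FAS. Dose reduction plays no part in it. The sensitivity analyses include a robust ANOVA with center and treatment.

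Two further analyses concern permanent dose reductions made because of an AE and recorded on the eCRF. One treats a subject as a dropout from the time of reduction. In the other, "another factor will be added to the robust ANOVA model to examine the effect of dose reduction", on the FAS. The SAP waives the analysis if fewer than 5% of subjects have a reduction in the first week. Protocol 13.1.3.1 has the same step with an ordinary model: "another factor will be added to the ANOVA model to examine the effect of dose reduction", with nobody excluded.

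On how reductions arise:
- Protocol 6.1, repeated in SAP 4.2, says that "with consideration to subject's bowel movement frequency and consistency, dose adjustments (dose reduction) may be made".
- Protocol 7.7 leaves AE-driven reduction to the investigator, including between visits.
- Appendix A lists optional reduction at Visits 3 and 4, nominally Days 8 and 15.

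Week 1 is the 168 hours from the first dose. Neither document says how the treatment coefficient from the augmented model is to be read.

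**The concern.** A factor in an ANOVA supports a comparison at a fixed level of that factor. This is harmless for something settled before randomisation, such as center. Dose reduction is settled afterwards and may depend on both the assigned drug and the bowel frequency that the model is trying to explain.

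Two things follow. First, the factor's coefficient mixes any effect of reducing the dose with the reasons for reducing it. If frequent bowel movements lead to reduction, reducers will show a high Week 1 count although reduction did not cause it. A reduction made after Week 1 has closed cannot have affected Week 1 at all. Second, the treatment coefficient becomes a comparison within reduction status, which is no longer the randomised comparison.

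At stake is interpretation. The model sits under sensitivity analyses of the primary endpoint, and it is fitted only when there are enough reductions to move the estimate.

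**Working it through.** **1. Inputs from SAP 6.0, checked on the plan's own figure.** "an alpha level of 0.05 for a 2-sided test", power 90%, "Assuming equal allocation", "a placebo mean of 4 (standard deviation of 2.7" and "a treatment mean of 5.9 (standard deviation of 4" (SDs in brackets).
- Pooled SD = √[(2.7² + 4²)/2] = √11.645 = 3.412; difference = 5.9 − 4 = 1.9.
- Normal approximation: 2 × (1.960 + 1.282)² × 11.645 / 1.9² = 67.8, so 68 per arm; the t-test needs 69.
- Dividing by the Wilcoxon efficiency 3/π: 69 × π/3 = 72.3, so 73 per arm.
- Total 2 × 73 = 146, which agrees with "a total sample size of 146 is required".

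The same means and SDs are used below.

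**2. The 5% threshold**, read as a share of all randomised subjects: 0.05 × 150 = 7.5, so at least 8 reductions. Rates of 10% on lubiprostone and 2% on placebo give 7.5 + 1.5 = 9 of 150, or 6%, just above it. Rates of 5% and 1% give 3.75 + 0.75 = 4.5, or 3%, and the model would not be run.

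**3. When the treatment coefficient moves.** Let D be dose reduction, p₁ and p₀ its rates on lubiprostone and placebo, and γ the fitted coefficient of D. For least squares, ignoring center,

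β(with D) = β(without D) − γ × (p₁ − p₀).

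There is no shift if D is unrelated to SBM within arm (γ = 0) or equally common in both arms. With p₁ − p₀ = 0.08, each SBM per week in γ moves the protocol's ordinary-ANOVA estimate by 0.08, which is 0.08/1.9 = 4.2% of the design difference. The robust fit downweights high counts, so its shift is found by simulation.

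**4. Size in the robust model.** Not in the documents and therefore assumed: reduction rates of 10% and 2%, and log-odds of reduction rising by 0.10 to 0.35 per SBM. Negative binomial counts, 200,000 per arm, Huber M-estimation with and without D:
- Without D: 1.59 SBMs per week.
- With D, log-odds 0.10: 1.49, a fall of 1 − 1.49/1.59 = 6.3%.
- With D, log-odds 0.35: 1.29, a fall of 1 − 1.29/1.59 = 18.9%.
- If reduction itself also lowers reducers' Week 1 count by an assumed 20–30%: between −1% and +2% at the low end, −12% to −15% at the high end.

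The high end is demanding: it implies reducers averaging roughly 5 to 6 more SBMs per week than non-reducers.

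**5. Other assumed mechanisms** (Tukey bisquare; log-odds ratio of 1.5 for treatment on reduction in every row):

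| Link to SBM, log-odds per SBM | Overall reductions | Without D | With D | Change |
|---|---|---|---|---|
| 0 | 10% | 1.545 | 1.549 | none |
| 0.15 | 5% | 1.550 | 1.436 | −7% |
| 0.15 | 15% | 1.537 | 1.176 | −23% |
| 0.3 | 5% | 1.521 | 1.285 | −16% |
| 0.3 | 15% | 1.553 | 0.918 | −41% |

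With no true drug effect on SBM, the two linked mechanisms still produce a treatment coefficient of −0.06 to −0.30 SBMs per week over 5–15% reductions. The direction is not universal. At 10% reductions with no selection on SBM, but with reduction lowering the count by 20%, the estimate rises from 1.390 to 1.469.

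**6. Timing.** The 168-hour week that starts on the morning of Day 1 closes on the morning of Day 8. A reduction at a nominal Day 8 or Day 15 visit comes at or after that. Unscheduled reductions, or a Visit 3 early in its two-day window, can fall inside Week 1, but they still follow part of the outcome. The readable SAP text applies the first-week limit to the threshold, not to the factor.

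**The case against.** The strongest case is that the factor is there to examine dose reduction and not to check the treatment effect. The treatment effect has its own analyses without the factor: the primary test, its per-protocol and worst-case repeats, and the robust ANOVA with center and treatment only. The FAS result regardless of reduction is already the primary result. This stands. A reader might infer that the plan biases the very effect the model is meant to check, but the text does not give the model that purpose. The reply is that the model fails on its stated purpose too, because γ is not an effect of reduction.

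Second, the SAP paragraph is scoped to permanent AE-driven reductions, so reductions made for bowel frequency alone may never enter the factor. This also stands. It may weaken the link with SBM, and the documents do not establish how strong the link is. It does not make the factor a baseline variable.

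Third, a reader might picture the strongest responders being dropped. They are not: all subjects stay in the model, and an additive factor averages contrasts within reduction status, reducers against reducers included.

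Fourth, the documents do not say that reduction is more common on lubiprostone. That, like every rate above, is an assumption.

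The empty brackets after the factor in the SAP may be text lost in conversion and are not counted against the plan.

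**Conclusion.** The point holds as a limited one. A planned analysis does not answer its own question: confounding and reverse causation prevent the dose-reduction coefficient from being read as the effect of reduction. The treatment coefficient from the same model can be biased, mainly toward placebo, if reduction is related to SBM within arm and its rate differs between arms.

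Under assumed rates of 10% and 2%, the fall is about 6% to 19%. It is little or nothing at the low end if reduction itself lowers Week 1 SBM, and zero if reduction and SBM are unrelated within arm. More frequent or more strongly outcome-driven reductions would give more. None of these sizes can be derived from the documents.

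A reader might go on to infer that the trial's conclusion is at risk. The documents do not support that: the van Elteren test and the sample size do not use the factor, SAP 7.8.2 rules out examining dose reduction for secondary endpoints, and a shift toward placebo would not create a false claim of benefit. The practical risk is that an attenuated coefficient is taken as a sign that the primary result is not robust.

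**What to change.** Remove the dose-reduction factor from the robust ANOVA. In its place, show Week 1 SBM frequency descriptively by arm for subjects with a reduction in Week 1. The primary FAS analysis, which includes these subjects, stays as it is.

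If the model is kept because the protocol specifies it, add to SAP 7.8.1 that it is descriptive only, that its treatment coefficient is not a sensitivity estimate of the treatment effect, and that only reductions within Week 1 count toward the factor.

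Cost: one model fewer and one small table more, or a few sentences. Removal is a departure from one protocol-specified exploratory model and should be documented before unblinding, for example in SAP 7.13. Sample size, the primary test and clinical conduct do not change.

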#### 7.8.2 Secondary Efficacy Endpoint(s)

The interaction of treatment and center and the effect of dose reduction will not be examined for any secondary endpoints. All secondary endpoints will be analyzed for the FAS only.

SBM frequency at Week 2, 3 and 4

The secondary endpoint will be analyzed as specified for the primary endpoint separately for each week.

Additionally for patients with a missing Week 2 frequency estimate (where diary days < 4 in Week 2) the Week 1 estimate will be carried forward, if available. For the worse-case analysis all missing Week 2 values will be assigned the lowest SBM frequency for week 2.

## Proportion of subjects with an SBM within 24 hours after first dose

The 24 hour period will be taken from the time of the first recorded dose in the patient diary. If the efficacy data is missing for the first 24 hours following this dose then it will be assumed that the patient did not experience any BM (including SBMs) during this period, this is based on the assumption that a patient is more likely to complete the diary on any particular day if they experience a BM than if they did not. The proportion of subjects with an SBM within 24 hours after first dose in Week 1 will be analyzed by a Cochran-Mantel-Haenszel (CMH) test stratified by center. Additionally a logistic regression model will be used with treatment and center as factors as a sensitivity analysis. The estimated odds ratio and associated 95% CI for both methods will be presented to aid interpretation of the clinical effect.

#### Mean Degree of Straining (Week 1, 2, 3, and 4)

For each BM patients should indicate the degree of straining associated with that BM. The degree of straining is a 5 point scale:

#### 0 = No straining

CROSS-REGIONAL TEMPLATE			
Template Number:	C-TMPL-DO-801	Page:	23 of 31
Version Number:	1.2	Effective Date:	14 Sep 2015
This version replace	s: 1.1		
Parent Document:	C-SOP-DO-800		
Template Title:	Statistical Analysis Plan (Legacy Takeda)	)	

1 = Mild straining

2 = Moderate straining

3 = Strong straining

4 = Very strong straining

For each subject, the mean degree of straining will be averaged for all SBMs in a given week. The mean degree of straining will then be analyzed by van Elteren tests, stratified by center, at Weeks 1, 2, 3, and 4 separately. A related 95% confidence interval and point estimate will be provided for the treatment difference; the confidence interval will be estimated by inverting the hypothesis test.

Additionally the endpoint will be analyzed using robust analysis of variance (ANOVA) models with center and treatment in the model as a sensitivity analysis.

If there are no SBMs during the week or if there are SBMs but all ratings are missing, then the LOCF method will impute the average from the average used for the most recent week. For Week 1 analysis where there is no value to carry forward then a value of 4 will be assumed. This assumption will be carried into later weeks if LOCF does not provide an estimate.

#### Mean Degree of Stool Consistency (Week 1, 2, 3, and 4)

For each BM patients should indicate the type of stool consistency associated with that BM. The degree of stool consistency is assessed using the Bristol Stool Scale [3]; a 7 point scale, where decreasing values indicate harder stools:

Type 1		Separate hard lumps, like nuts (hard to pass)
Type 2		Sausage-shaped but lumpy
Туре 3		Like a sausage but with cracks on its surface
Type 4		Like a sausage or snake, smooth and soft
Type 5	666	Soft blobs with clear-cut edges (passed easily)
Type 6	-98	Fluffy pieces with ragged edges, a mushy stool

CROSS-REGIONAL TEMPLATE			
Template Number:	C-TMPL-DO-801	Page:	24 of 31
Version Number:	1.2	Effective Date:	14 Sep 2015
This version replaces	s: 1.1		
Parent Document:	C-SOP-DO-800		
Template Title:	Statistical Analysis Plan (Legacy	y Takeda)	
			7

Stool consistency will be analyzed in the same manner described for the degree of straining. For Week 1 analysis where there is no value to carry forward then a value of 1 will be assumed. This assumption will be carried into later weeks if LOCF does not provide an estimate.

## Weekly Abdominal Symptoms Score (Bloating and Discomfort) (Week 1, 2, 3, and 4)

The abdominal symptom score should be completed by patients in their diary, every 7 days on the last day of each treatment week upon waking in the morning. Patients should indicate the degree of abdominal bloating and discomfort experienced over the past week.

Abdominal Bloating	0 = None: No abdominal distension	
	1 = Mild: Slight abdominal distension	
	2 = Moderate: Abdominal distension clearly felt	
	3 = Severe: Severe abdominal distension	
	4 = Very severe: Extremely strong abdominal distension	
Abdominal Discomfort	0 = None: No abdominal discomfort	
	1 = Mild: Slight abdominal discomfort	
	2 = Moderate: Abdominal discomfort clearly felt	
	3 = Severe: Abdominal discomfort with pain	
	4 = Very severe: Abdominal discomfort with severe pain	

The abdominal symptoms (bloating and discomfort) will be analyzed separately by van Elteren tests, stratified by center, at Weeks 1, 2, 3, and 4. A related 95% confidence interval and point estimate will be provided for the treatment difference; the confidence interval will be estimated by inverting the hypothesis test.

Additionally a cumulative logistic regression model will be used with treatment and center as factors as a sensitivity analysis. The estimated odds ratio and associated 95% CI will also be presented to aid interpretation of the clinical effect. The interaction between treatment and center will also be examined in a separate model.

If the assessment ratings are missing, then the LOCF method will impute the value from the value used for the most recent week. For Week 1 analysis where there is no value to carry forward then a value of 4 will be assumed. This assumption will be carried into later weeks if LOCF does not provide an estimate.

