#### 6.0 STUDY DESIGN AND DESCRIPTION

# 6.1 Study Design

This is a phase 3, randomized, double-blind, parallel-group, placebo-controlled study in subjects with CIC as determined by the Rome III Diagnostic Criteria for Functional Constipation [4]. This study consists of a 14-day Screening Period and a subsequent 4-week (28 days) Double-Blind Treatment Period in which subjects will receive either lubiprostone or matching placebo BID. Subjects will be randomized to either active lubiprostone or placebo in a 1:1 ratio.

During the Screening Period, the defecation behavior of each subject is recorded in a diary to confirm he/she has constipation. Use of all existing laxatives is stopped at the beginning of the Screening Period (Visit 1). Subjects are instructed not to change their diet or lifestyle habits during the study. A total of 10 mg of bisacodyl suppository (or any equivalent drug) may be prescribed as a standard rescue medication if a subject has no adequate bowel movement for 3 consecutive days during the Screening Period of the study. When bisacodyl suppository does not improve constipation, glycerin enema (or equivalent drug) will be given. Subjects are instructed to complete their diaries before using rescue medications.

The subject diary will be distributed on Study Days -15, -1, 8 and 15. Subjects will be instructed to keep the diary every day including on the morning of Visit 1.

If the rescue medications fail to improve constipation, the investigator may decide to use another rescue medication. The recommendation may include a medication from the excluded medication list other than any form of polyethylene glycol (PEG), linaclotide, methylnaltrexone, or prucalopride, all of which are considered prohibited rescue medications. No rescue medication may be given 24 hours prior to and until 48 hours after the first dose of the study drug (Day 1). Subjects who use a rescue medication within 24 hours before the first dose of study drug on Day 1 should be withdrawn from the study. Those who use a rescue medication within 48 hours after dosing on Day 1 will be discontinued from the study by the investigator. The dose and mode of administration of rescue medications must be recorded in the electronic case report form (eCRF).

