#### 9.1.7.5 Assessments of Abdominal Symptoms

The abdominal symptoms (bloating and discomfort upon waking in the morning) will be scored weekly on a 5-point scale, with a higher score indicating more severe symptoms. This will be assessed at Baseline and at Weeks 1, 2, 3, and 4. Subjects will be instructed to record weekly abdominal symptoms assessment in the diary. Diary entries will be reviewed at each study visit as per protocol schedule.

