#### **Study Visit Windows**

For BM data the assignment of data to each week (1, 2, 3 and 4) will be calculated from the date and time of the morning dose on Day 1. If no morning dose was taken on Day 1, then the date of Day 1 will be used and the time of the first recorded morning dose will be used. Weeks will be calculated as 168-hour intervals starting from this time. Note that any diary entries prior to this will be assigned to the screening period. Where missing dates or times do not allow the assignment of diary data to a treatment period (Screening or double blind) then it will be assumed that all data in the Screening booklet was recorded during Screening and all data in the remaining booklets were recorded after the booklets were provided to subjects. Abdominal symptom assessments will be assigned to the week as recorded in the diary. PAC-QOL is assessed at Day -1, Week 2 (Day 15) and Week 4 (Day 29). PAC-QOL assessments will be assigned to the time point relating to the visit at which they are recorded, regardless of actual study day. Assessments conducted at an Early Termination Visit will be assigned to the next scheduled visit that would have taken place if the subject had not discontinued, e.g. if the subject withdraws prior to Week 2 then the Early Termination Visit assessment will map to Week 2, whereas if the Early Termination Visit occurs after Week 2 then the assessment will be assigned to Week 4.

	Sc	creening	Double Blind Treatment Period				
Study Day/Week	Screening	Randomization	First Dose	Week 1	Week 2	Final Visit / Early Termination Visit Week 4	Follow-up Phone Contact
Visit Number:	1	2	-	3	4	5	-
Day	-15	-1	1	8	15	29	43

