Parent Document:	C-SOP-DO-800			
Template Title:	Statistical Analysis Plan (Legacy Takeda)	1		

The number of capsules taken is derived from the subject diary and will be calculated as the number of completed dosing entries in the diary for the first 7 days following randomization (i.e. Day 1 to Day 7 inclusive). This should be 2 per day, a morning and evening dosing record).

The number of expected capsules to be taken will be calculated as 14 (7 days of BID dosing) if the subject has not withdrawn prior to completing 7 days of dosing. If the subject has withdrawn early (less than 7 days on treatment) then this number will be calculated as for overall compliance.

Overall study drug compliance should also be calculated from the subject's diary, where the number of tablets taken is derived from the number of completed entries (there should be 2 per day, a morning and evening record). The number of expected capsules is calculated as before. If there is a discrepancy between calculated compliance values then unless there is a recorded comment explaining the discrepancy and indicating that the diary value is correct (e.g. a comment may have been recorded indicating that some tablets were lost) the overall compliance calculated using capsule counts will be taken as the correct value.

Study drug compliance will be summarized, for overall compliance and for compliance during Week 1, as a continuous variable and additionally, as a categorical variable, with the following categories:

- Compliance < 70%
- Compliance  $\geq$  70% and < 90%
- Compliance  $\geq$  90% and < 110%
- Compliance >110%

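### As the SAP words it, the Week 1 bloating and discomfort score most naturally recalls about one day before the first dose, while the Week 2 to 4 scores recall none

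*SAP*

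**What the plan says.** - **When the score is completed.** SAP 7.8.2 has the two items filled in "every 7 days on the last day of each treatment week upon waking in the morning". No study day is named.
- **What the patient is asked.** The same section says: "Patients should indicate the degree of abdominal bloating and discomfort experienced over the past week".
- **When treatment starts.** Protocol 6.1: "Subjects are to begin their study drug treatment in the morning with breakfast following Visit 2". The note to Figure 6.a places randomization on Day -1 and adds: "The first dose of study drug is administered the next day, on Day 1 of the Double-Blind Treatment Period".
- **How weeks are counted.** Protocol 6.1 has a "4-week (28 days) Double-Blind Treatment Period". SAP 7.7, for Week 1 drug compliance, uses the "first 7 days following randomization (i.e. Day 1 to Day 7 inclusive".
- **How scores are assigned to weeks.** The Study Visit Windows text in SAP 7.1 says of bowel movement data: "Weeks will be calculated as 168-hour intervals starting from this time". It handles abdominal scores separately, by the week marked in the diary.
- **How the protocol describes the endpoint.** Protocol 9.1.7.5: "The abdominal symptoms (bloating and discomfort upon waking in the morning) will be scored weekly on a 5-point scale". Protocol 13.1.3.2 also ties the symptoms to waking. Neither section gives a past-week recall.
- **How the scores are used.** SAP 7.8.2 tests bloating and discomfort separately by van Elteren test at each of Weeks 1 to 4. A missing score takes the most recent week's value. SAP 7.8 asks for box plots from baseline to Week 4.

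**The concern.** A past-week question answered on the morning of the last day of a week does not cover that week. It omits the last day and takes in the day before the week began. In Weeks 2 to 4 the extra day is an earlier treated day. In Week 1 it is Day -1, before any drug was taken, which SAP 7.8 itself counts as baseline for diary data.

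Two secondary Week 1 comparisons would therefore include untreated time and tend to understate a drug effect. Because missing scores are carried forward, a subject lacking a Week 2 score would take that Week 1 value with them. Nothing in either document acknowledges the overlap or corrects for it.

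A second problem sits beneath this one. The SAP treats waking as the time of completion and asks about a week. The protocol can be read as asking about symptoms on waking. These are different measurements.

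**Working it through.** The documents give no power or effect size for these scores, so there is no planned figure to reproduce. The check is a timeline.

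**Inputs.** First dose with breakfast on Day 1, the day after Day -1, with no Day 0 (protocol 6.1). Four weeks in 28 days (protocol 6.1), with Week 1 as Days 1 to 7 (SAP 7.7). The last days of the weeks are then Days 7, 14, 21 and 28. Recall of seven days, or 168 hours (SAP 7.8.2). Clock times are not in the documents; I assume breakfast dosing 0.5 to 2 hours after waking.

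**Recall window.** It ends on waking on the scoring day and starts seven days earlier.

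| Score | Ends on waking, Day | Starts on waking, Day | Pre-dose days of 7 |
|---|---|---|---|
| Week 1 | 7 | -1 | about 1 |
| Week 2 | 14 | 7 | 0 |
| Week 3 | 21 | 14 | 0 |
| Week 4 | 28 | 21 | 0 |

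**Week 1 in hours.** Pre-dose time = 24 + gap from waking to first dose = 24.5 to 26 hours. As a share: 24.5/168 = 14.6% to 26/168 = 15.5%.

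**Alternative reading.** If the score were completed on waking on Day 8, the pre-dose time would be the gap alone: 0.5/168 = 0.3% to 2/168 = 1.2%.

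**Dilution.** Let d1 to d7 be the treatment difference on Days 1 to 7, and suppose that recall averages the days evenly. The full Week 1 difference is (d1 + ... + d7)/7. The score captures (0 + d1 + ... + d6)/7, since the expected difference on Day -1 is zero. The ratio is 1 - d7/(d1 + ... + d7).

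- Equal effect each day: 6/7 = 0.857.
- Effect building linearly (1, 2, ..., 7): 21/28 = 0.75.
- Effect waning linearly (7, 6, ..., 1): 27/28 = 0.964.
- Equal effect, but recall weights rising 1 to 7 from the oldest day to the newest: 1 - 1/28 = 0.964.

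Dilution is thus worse if the effect builds, and milder if it wanes or recall favours recent days. The shift is toward no difference provided the Day 7 effect favours the drug and the oldest day carries some weight.

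**The case against.** **Day 7 is inferred.** This is fair. SAP 7.8.2 gives no day number, and diary-keeping runs to Day 29 (protocol Appendix A), so scoring on waking on Day 8 would be workable and would nearly remove the problem. But Day 8 is not the last day of a week counted as Days 1 to 7, and nothing in the SAP points to it for this score. The ambiguity is itself a reason to number the days.

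**The protocol wording may imply no weekly recall.** Also fair: on that reading no pre-dose day enters. The SAP nevertheless states a past-week recall, so the two must be reconciled. Appendix E is only a sample of the diary, and its silence on recall does not show that the diary in use is silent.

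**The scores are out of step with the 168-hour weeks.** A reader might infer that every weekly score is mislabelled by a day against the weeks used for bowel movement frequency. The documents do not support this. The 168-hour rule is written for bowel movement data, and symptom scores follow the diary's own week.

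**A rise from Week 1 to Week 2 would be misread.** Each week is tested separately between arms, no between-week test is planned, and the box plots are descriptive. What remains is a caution when reading the plots.

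**Conclusion.** The point stands as a small, inexpensive improvement. On the most natural reading of SAP 7.8.2, about one of the seven days recalled in the Week 1 score precedes the first dose; Weeks 2 to 4 have none. With even recall and an equal daily effect, the Week 1 difference is about 6/7 of its full size. The illustrative patterns above run from 0.75 to 0.96. These figures depend on the Day 7 reading and on patients recalling a strict seven days.

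Both randomized arms answer over the same window, so the Week 1 tests keep their type I error. The primary endpoint is unaffected. At issue is one of four time points for one pair of secondary symptoms.

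A reader might convert 6/7 into a loss of power. The documents do not support a figure: the plan states no power for these scores, and the conversion would need an averaged response with unchanged variance, whereas each score is a single 5-point ordinal rating analysed by ranks.

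Separately, and whichever day is meant, the protocol and SAP do not describe the same measurement.

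**What to change.** 1. Word the Week 1 diary item as symptoms since the first dose of study drug. Keep past-week recall for Weeks 2 to 4.
2. Name the scoring days by study day (Days 7, 14, 21 and 28 if the present scheme is kept).
3. State the same recall period in the diary, protocol 9.1.7.5 and 13.1.3.2, and SAP 7.8.2, and say whether waking is the time of completion or the moment being rated.

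This costs a diary wording change and a sentence or so in each place, with no new assessment. The downside is that the Week 1 recall covers six days, not seven.

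Moving the score to waking on Days 8, 15, 22 and 29 is an alternative, but only with protection against early visits. Protocol 9.3 allows visits within 2 days of schedule, and protocol 9.1.17 has diaries collected at them. A Visit 3 on Day 6 or 7 would take the diary before a Day 8 score. A final visit on Day 27 or 28 would come before a Day 29 score, with no later diary to hold it.
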